4.7.4 Vital Signs Assessments

Vital signs, including systolic (SBP) and diastolic blood pressure (DBP), heart rate, respiration rate, and oral temperature are measured at the time points indicated in the SOA (Table 1). Vital signs (except for height and weight and BMI collected at Screening only) will be monitored periodically during and following study of drug administration. The investigator may repeat the vital signs if deemed appropriate.

All assessments will be listed by participant, treatment sequence, and visit.

A summary table will be produced and will include descriptive statistics for baseline, post-baseline, and change from baseline values by treatment sequence for each vital sign parameter (this will not include BMI which is calculated at screening).

4.7.5 Physical Examinations

A complete physical examination (PE) will be conducted at the time points designated in the schedule of assessments (SOA) (Table 1). At other designated time points, a partial (symptom-directed) physical examination may be conducted.

A full PE includes assessment of general appearance, skin, HEENT (head, eyes, ears, nose, and throat), neck (including thyroid and nodes), cardiovascular, respiratory, gastrointestinal, and neurological.

Physical examinations may be repeated prior to study discharge as deemed necessary by the Investigator or in response to AE.

Physical examination results will be listed by participant, treatment, and visit.

4.7.6 Electrocardiogram

Electrocardiograms (ECGs) will be performed at screening, admission, pre-dose, on dosing days Day 1 in each period (3–6h post-dose, approximate C_{max}), and on Day 15 or at the early termination (ET) visit with all measurements taken within 5 minutes apart. ECG time points are indicated in the SOA (Table 1). The date and time of each ECG and its results will be documented in the source documents and transcribed into the eCRF.

Electrocardiograms may be performed at any time during the study in the interest of subject's safety at the discretion of the Investigator.

The overall interpretation of the ECG result will be presented as normal, abnormal (not clinically significant) and abnormal (clinically significant) for each day, by treatment. Descriptive statistics will be presented for the ECG measurements and change from baseline collected each day by treatment sequence.

The ECG parameters will be listed by participant, treatment sequence, and visit.

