### Statistical Methods:

The sample size has been selected in accordance with standard designs for Phase 1 assessments of PK, safety, and tolerability. The primary analysis will describe the PK characteristics of the two drug products. PK samples will be collected at pre-specified time points.

The PK parameters to be assessed include but are not limited to:

- Cmax maximum plasma concentration
- Cmin0-24 minimum plasma concentration from time zero to 24 hours post-dose
- tmax time of maximum plasma concentration
- λz terminal-phase rate constant
- t½ elimination half-life
- AUC0-24 area under the plasma concentration-time curve from time zero to 24 hours post-

	dosing
• $AUC_{0-t}$	area under the plasma concentration-time curve from time zero to time t (time of last quantifiable plasma concentration)
• $AUC_{0-\infty}$	area under the plasma concentration-time curve from time zero to infinity
• $CL/F$	apparent clearance
• $MRT$	mean residence time
• $V_z/F$	apparent volume of distribution

The secondary endpoints will describe the incidence of adverse events and laboratory abnormalities. Adverse events will be coded according to system organ class and preferred term using the Medical Dictionary for Regulatory Activities (MedDRA) (version 25.1 [released September 2022] or the current version). Their severity will be graded using the National Cancer Institute Common Terminology Criteria for Adverse Events (NCI CTCAE) 5.0 or the current version. Adverse events will be organized by system organ class and preferred term. The vital signs, ECG findings, and physical examination data and change of hematologic and chemistry parameters from baseline will be summarized for each post-baseline visit. Hematologic and chemistry parameters will be categorized as low, normal, or high based on laboratory normal ranges and presented as shifts from baseline. A detailed description of data analyses and statistical methods will be outlined separately in the Statistical Analysis Plan.
	
Date: 29 January 2025	

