### 4.1. Participant Inclusion Criteria

Participants meeting all the following criteria are eligible for study participation:

1. Is male or female, age 18 to 45 years, inclusive, at Screening.
2. Body mass index (BMI) between 18 and 35 kg/m^2, inclusive, at Screening.
3. In good general health, determined by no clinically significant findings in the opinion of the Investigator from medical history, physical examination, 12-lead ECG, clinical laboratory findings, and vital signs at Screening and Day -1 or 1.
4. Hemoglobin, hematocrit, white blood cell count, absolute neutrophil count, and platelet count results within the laboratory reference range at Screening or without clinically significant abnormalities in the opinion of the Investigator; participants with Gilbert's disease with associated abnormalities of liver function tests are eligible for enrollment. Tests may be repeated at the discretion of the Investigator to confirm abnormalities.
5. Estimated glomerular filtration rate (eGFR) based on the Chronic Kidney Disease Epidemiology Collaboration (CKD-EPI) equation of  $\geq 80$  mL/min/1.73 m^2 at Screening.
6. Females of childbearing potential must practice effective contraception per national regulatory guidelines for clinical trials from Screening (see Section 5.6.2), throughout the study, and for 60 days after the last dose of study drug.
7. Females must have a negative pregnancy test at Screening and within 24 hours prior to dosing of study drug; for post-menopausal participants, a blood sample will also be tested for estradiol and follicle stimulating hormone (FSH) to confirm post-menopausal status based on reference laboratory ranges for post-menopausal status. Surgically sterile females are eligible; however, proof via medical records will be required.
8. Males must agree to not donate sperm and to use condom and spermicide in combination with any of the means of contraception for their female partners detailed in Section 5.6.2 during sexual intercourse from the time of the first study drug administration and for

90 days following the last dose of study drug. Females must agree not to donate eggs from the time of the first study drug administration and for 60 days following the last dose of study drug.

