#### **4.2. Participant Exclusion Criteria**

Participants meeting any of the following criteria are not eligible for study participation:

1. Any clinically significant underlying illness in the opinion of the Investigator.
2. Poor venous access.
3. Prior exposure to ARN-75039.
4. History of drug or alcohol abuse within 1 year of Screening in the opinion of the investigator, or a positive test for drugs of abuse or alcohol at Screening or Day -1.
5. Use of any prescription or over-the-counter (OTC) medications, including food supplements, vitamins, herbal medications (e.g., St. John's wort), and cannabis, with the exception of contraceptive medications and as needed (prn) acetaminophen or paracetamol (not exceeding 2 grams/day) within 7 days prior to study drug administration and through the Day 15 Discharge visit.
6. Any female who is pregnant or breastfeeding, or any female who is planning to become pregnant during the study and safety follow-up period.
7. Currently enrolled in another investigational device or drug study, or less than 30 days or 5 half-lives of the prior investigational agent (whichever is longer) or plans to enroll in another investigational device or drug study during the course of this study.
8. Inability to ingest all capsules of a multi-capsule dose within 5 minutes of ingestion of the first capsule.
9. Positive serology for hepatitis B virus (HBV), hepatitis C virus (HCV), or human immunodeficiency virus (HIV) at Screening; participants with adequately treated HCV are eligible for enrollment.
10. Consumption of Seville oranges, grapefruit or grapefruit juice within 72 hours prior to Day 1 or during the study.
11. History of malignancy, except adequately treated basal cell carcinoma or in situ carcinoma of the uterine cervix.

12. Smoking cigarettes, cigars, cigarillos or E-cigarettes
13. Any reason or condition that, in the investigator's opinion, may compromise study participation, present a safety risk to the participant, or may confound the interpretation of the study results.
14. A QT duration corrected for heart rate by Fridericia's formula (QTcF) > 450 millisecond (msec) based on either single or averaged QTcF values of triplicate ECGs obtained over a 3-minute interval (at Screening).
15. Blood product (including plasma) donation within 30 days before Screening.
16. Unwilling to consume a breakfast on study drug administration days.
17. History of:

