### **7.8. Safety Analysis**

Safety will be assessed by evaluation of AEs, physical examinations, clinical laboratory evaluations, ECGs, and vital signs measurements. AEs will be coded by system organ class and preferred term using the Medical Dictionary for Regulatory Activities (MedDRA) (version 25.1

[released September 2022] or the current version). The occurrence of TEAEs and AESIs will be presented by system organ class and preferred term by treatment. Additionally, TEAEs and AESIs will be presented by treatment for each relationship and severity with the most closely related or most severe presented for events that occurred more than once. A listing of SAEs will be provided, if applicable.

Physical examination findings will be provided in a data listing.

The overall interpretation of the ECG result will be presented as normal, abnormal (not clinically significant) and abnormal (clinically significant) for each day, by treatment. Descriptive statistics will be presented for the ECG measurements and change from baseline collected at each day by treatment.

For the continuous laboratory parameters, descriptive statistics will be presented for each day and for the changes from baseline to each day by treatment. Additionally, parameters will be categorized as low, normal, or high according to laboratory range specifications and the number and percentage of participants will be presented by treatment.

For each vital sign measurement and changes from baseline at each time point, descriptive statistics will be presented by treatment.

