2.3 Endpoints

Primary:

- Relative bioavailability comparison of 300 mg neat ARN-75039 in HPMC capsules (Treatment A; reference) to 300 mg ARN-75039 with excipients tablets (Treatment B; comparator) following oral administration under fed conditions.
- PK parameters of 300 mg ARN-75039 with excipients tablets and 300 mg neat ARN-75039 in HPMC capsules, including but not limited to:
 - Area under the plasma concentration-time curve from time zero to time of last quantifiable concentration (AUC_{0-t}).
 - Area under the plasma concentration-time curve from time zero to 24 hours post-dose (AUC_{0-24}).
 - Area under plasma concentration-time curve from time zero to infinity ($AUC_{0-\infty}$).
 - Maximum observed plasma concentration (C_{max}).

- Minimum observed plasma concentration from time zero to 24 hours post-dose $C_{min0-24}$.
- Time to reach C_{max} (t_{max}).
- Half-life ($t_{1/2}$).
- Apparent clearance after extravascular administration (CL/F).
- Apparent volume of distribution during the terminal phase after extravascular administration (V_z/F).

Secondary:

- Type and frequency of treatment-emergent adverse events (TEAEs).
- Type and frequency of treatment-emergent serious adverse events (TESAEs).
- Type and frequency of study drug-related >Grade 1 TEAEs.
- Type and frequency of changes in clinical laboratory values, ECGs, colonic transit time (biomarker), physical examinations, and vital signs.

3 Study Design and Methods

ARN-75039-103 is a comparative, randomized, single-dose, crossover study to assess the PK, safety, and tolerability of neat ARN-75039 in hydroxypropyl methylcellulose (HPMC) capsules against ARN-75039 with excipients in tablet form administered by the oral route in healthy adult participants. The safety assessments will include assessments of vital signs, clinical laboratory values, and ECGs.

A total of 16 participants were randomized 1:1 into one of the following two sequences:

Sequence 1:

[figure not shown]
- Period 1: 300 mg neat ARN-75039 in HPMC capsules (Treatment A; reference product)
- Period 2: 300 mg ARN-75039 with excipients in tablet form (Treatment B; comparator)

Sequence 2:

- Period 1: 300 mg ARN-75039 with excipients in tablet form (Treatment B; comparator)
- Period 2: 300 mg neat ARN-75039 in HPMC capsules (Treatment A; reference product)

A study scheme is provided below:

Sequence 1

Sequence 2

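### The qualitative ECG read is tabulated as status per day, which does not count changes from baseline; a shift table by formulation should be added (minor)

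*SAP*

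**What the plan says.** - **Endpoint.** SAP 2.3 lists as secondary "Type and frequency of changes in clinical laboratory values, ECGs, colonic transit time (biomarker), physical examinations, and vital signs".
- **Qualitative read.** SAP 4.7.6 says the overall interpretation "will be presented as normal, abnormal (not clinically significant) and abnormal (clinically significant) for each day, by treatment". Protocol 7.8 has the same sentence: "The overall interpretation of the ECG result will be presented as normal, abnormal (not clinically significant) and abnormal (clinically significant) for each day, by treatment".
- **Measurements.** The next sentence of SAP 4.7.6 adds: "Descriptive statistics will be presented for the ECG measurements and change from baseline collected each day by treatment sequence". Protocol 7.8 plans this by treatment.
- **Entry.** Inclusion criterion 3 (protocol 4.1) reads "In good general health, determined by no clinically significant findings in the opinion of the Investigator from medical history, physical examination, 12-lead ECG", assessed with laboratory findings and vital signs at Screening and Day -1 or 1. The only numerical ECG exclusion (protocol 4.2, criterion 14) is a QTcF above 450 msec at Screening.
- **Baseline.** SAP 3.4 defines it separately for each period, as the value before that period's dose.
- **Schedule.** Table 1, footnote f, sets triplicate ECGs pre-dose and at 1, 3, 6, 8, 24, 48 and 72 hours after each dose.
- **Laboratory categories.** The protocol synopsis has these "categorized as low, normal, or high based on laboratory normal ranges and presented as shifts from baseline". No such wording appears for the ECG interpretation in either document.

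**The concern.** The endpoint asks how often something changed. A status table answers how many participants were in each category on a given day. The two agree only if nobody is abnormal at baseline, and the eligibility criteria do not ensure that.

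A participant who enters with a non-significant abnormality that persists is counted as abnormal on every ECG day. One participant's new abnormality can be offset by another's resolved one, and the daily count stays the same. In Period 2 the entry criteria no longer protect the baseline. Protocol 3.2 itself describes the half-life as long and the washout as relatively short, so a finding that arose in Period 1 and persisted to Day 8 would appear under the second formulation although it preceded that dose.

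At stake is a usable count, by formulation, of participants whose ECG read worsened after dosing.

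**Working it through.** The plan states no figure for this table, so there is nothing to reproduce. The check is what the daily counts can and cannot determine.

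**Inputs**
- N = 16 participants (SAP 3 and 3.3).
- Two states: normal, or abnormal of either kind.
- b = number abnormal at the period baseline, and p = number abnormal at a post-dose assessment. The documents give neither, so the values below are assumptions.
- k = number abnormal at both. A status table does not show it.

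**Formulas**
- k lies between max(0, b + p − 16) and min(b, p).
- Newly abnormal = p − k, which lies between max(0, p − b) and min(p, 16 − b).
- Any change = b + p − 2k.
- Width of the newly abnormal range = min(b, p) − max(0, b + p − 16), which is never more than b.

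**Results over assumed counts**

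| b | p | Range of k | Newly abnormal | Any change |
|---|---|---|---|---|
| 0 | 2 | 0 | 2 | 2 |
| 2 | 2 | 0–2 | 0–2 | 0–4 |
| 4 | 4 | 0–4 | 0–4 (0–25%) | 0–8 |
| 4 | 5 | 0–4 | 1–5 (6–31%) | 1–9 |
| 4 | 6 | 0–4 | 2–6 | 2–10 |
| 8 | 8 | 0–8 | 0–8 | 0–16 |

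With b = 0 the count is exact. With b = 1 the range spans at most one participant.

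**Which categories are affected.** Criterion 3 bars clinically significant findings at entry, so a clinically significant read in Period 1 is largely new. The ambiguity in Period 1 is therefore between normal and abnormal not clinically significant. In Period 2 it can affect any category.

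**Which read is counted.** On Days 1 and 8 the schedule has 5 ECG time points (pre-dose, 1, 3, 6 and 8 hours) × 3 recordings = 15 recordings. A count for each day does not say which of them supplies the category. Baseline and post-dose reads share that day, so the table may not show b and p separately. The ranges above assume that it does.

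**After the fix.** A cross-tabulation of baseline against post-dose category observes k directly, so each range becomes one number.

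**The case against.** The strongest reply is that ECG change is already analysed. That is right for the measurements: SAP 4.7.6 plans descriptive statistics of change from baseline. A reader might infer from the status table that the plan ignores ECG change, or that the QTc and heart-rate effects seen in dogs would go unexamined. The documents do not support this. Those signals are quantitative and belong to the measurement summary, and protocol 1.2.8 reports no waveform abnormality or arrhythmia on the qualitative read in dogs. Still, means and standard deviations of change are not a frequency, and interpretation categories have no mean.

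A reader might also infer that the formulations cannot be compared on new findings. That is too strong. In participants who complete both periods, a stable old abnormality adds equally to both formulations. SAP 4.7 also says that all safety assessments will be listed, so with 16 participants new abnormalities could be counted by hand. What is missing is a planned tabulation of a stated endpoint.

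Nor does the SAP treat ECGs less carefully than laboratory tests. The shift wording is in the protocol synopsis only: protocol 7.8 gives number and percentage by laboratory category, and SAP 4.7.3 gives flags and descriptive statistics. On the interpretation table the SAP matches protocol 7.8, so there is no conflict between the documents.

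Finally, neither document spells out the table layout. The SAP leaves it to the table shells, which are not among the documents reviewed. A shift table may exist there, but the SAP text does not ask for one.

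**Conclusion.** The point holds for the qualitative ECG interpretation only. As written, the per-day status presentation does not give the frequency of changes that SAP 2.3 names. The resulting uncertainty in newly abnormal participants is at most the number abnormal at baseline. It is nil if there are none, and 0 to 4 of 16 in the example of 4 before and 4 after. That example is an illustration, because the documents give no baseline count and these are healthy adults aged 18 to 45. The conclusion assumes that the table reports counts of participants per category and that the shells add no shift table.

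Severity is minor: the endpoint is secondary and descriptive, and neither the sample size nor the primary pharmacokinetic comparison is affected.

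**What to change.** In SAP 4.7.6:

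1. Keep the by-day status table. Protocol 7.8 commits to it, and replacing it would create a discrepancy.
2. Add a shift table by formulation. Rows are the pre-dose category of that period (baseline as in SAP 3.4). Columns are the category at each scheduled post-dose time point and, separately, the worst post-dose category.
3. Report the number and percentage of participants who moved to a worse category, for each formulation.
4. State one rule for combining the three reads of a triplicate into one category, and use it for baseline and post-dose alike.
5. State whether the Day 7 and Day 15 ECGs in Table 1 count as post-dose reads of Periods 1 and 2.

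The cost is a few SAP sentences and one more table shell. No ECGs are added and the sample size does not change. One drawback should be noted under the table. The worst post-dose column compares one baseline read with the worst of up to seven reads (1 to 72 hours), so ordinary variability overstates absolute worsening. The number of scheduled reads is the same for both formulations, so this applies equally to each, and the per-time-point columns are free of it.

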4.8 Interim Analysis

No interim analysis is planned.

4.9 Statistical Programming and Deliverables

All statistical analyses, tables, and listings will be generated in SAS (version 9.4 or later) with appropriate documentation and programming validation. The table of contents of all tables, listings, and figures will be presented in a TLFs shell supplemental document.

4.10 Changes to the Planned Analysis

Any deviation(s) of consequence from the SAP during the data analysis will be documented and justified in an amended SAP and/or in the final report or addressed in a separate document (such as the Clinical Study Report), as appropriate.

5 Revision history (for any changes post-Final SAP)

Version	Date	Comments
